3.4 Guidelines for Evaluation of Measurable Disease

- **Clinical lesions** will only be considered measurable when they are superficial (e.g skin nodules, palpable lymph nodes).
- **Chest X-ray** lesions are acceptable as measurable lesions when they are clearly defined and surrounded by aerated lung. However, CT is preferable.
- **Conventional CT and MRI** should be performed with cuts of 10mm or less in slice thickness contiguously. Spiral CT should be performed using a 5mm contiguous reconstruction algorithm. This applies to the chest, abdomen, and pelvis. Head & neck and extremities usually require specific protocols.
- **Ultrasound** should not be used to measure tumor lesions that are clinically not easily accessible when the primary endpoint of the study is objective response evaluation. It is a possible alternative to clinical measurements of superficial palpable nodes, subcutaneous lesions and thyroid nodules. US might also be useful to confirm the complete disappearance of superficial lesions usually assessed by clinical examination
- **PET/CT** may be performed as an alternative to CT or MRI at the investigator's discretion

3.5 Correlative Science

All correlative studies will be performed upon completion of the trial as a batch run.

The correlative studies detailed below may be altered at the discretion of the Principal Investigator.

3.5.1 FcR Polymorphism

Genomic polymorphisms corresponding to phenotype expression of valine (V) or phenylalanine (F) at amino acid 158 on the Fc γ RIIIa will be analyzed fluorescent automated cycle sequencing of Taq PCR products

3.5.2 Peripheral Blood FACS Analysis

PBMCs will be subjected to FACS analysis for expression of CD3, CD4, CD8, CD25, CD39, CD73, CD127, FOXP3, CD122, CD212 (IL-12R), HLA-DR, CD14, CD19, CD56, CD69, FAS-L and granzyme B as well as additional antigens as indicated. Flow cytometry to detect

intracellular cytokine production in individual cells in peripheral blood, or from cells in the ELISA assays will also be performed to test production of IL-2, IL-10, interferon- γ , TGF- β and other cytokines as indicated.

Treg function will be determined following isolation of CD4 $^{+}$ CD25 $^{+}$ cells from PBMC using published criteria. CD 39 and CD73 will be used to identify memory T reg cells. Functional tests include inhibition of T cell proliferation driven by α -CD3 plus α -CD28 mAb exposure, reduction in T cell IL-2 or interferon- γ production and reduced cytolytic activity. Sorting of cells into additional populations (LAG3 $^{+/-}$, CD27 $^{+/-}$, CD8 $^{+/-}$, Ki-67 $^{+/-}$) may also be attempted prior to suppression testing. *Foxp3* message will be ascertained by flow cytometry. If primary tissue is available, IHC for CD3, CD4, CD8, FOXP3, and CD56 will be performed.

3.5.3 Plasma Cytokine Analysis

Samples will be saved until the end of study for a batch run. At that time, cytokines will be tested using commercial ELISA kits (R&D Systems, Minneapolis, MN). Cytokines to be tested include interferon- γ , GM-CSF, sIL-2R, IL-2, IL-4, IL-10, IL-12, Rantes and TGF- β .

3.5.4 Minimal Residual Disease Analysis

If a paraffin embedded diagnostic tissue specimen is available, this material will be used to generate patient specific probes for detection of minimal residual disease in blood at baseline and during protocol therapy (at the end of Part I, prior to starting Cycle 6, and at the investigator's discretion in subjects who experience a durable remission) using a PCR assay. This assessment will be performed using a portion of the peripheral blood collected for ancillary studies (see Section 3.5.3) and will not require blood collection beyond that performed during the study for other analyses.

3.6 Correlative Science Sample Submission

3.6.1 FcR Polymorphism Sample Procurement (Cohort 1 Only)

If a patient has consented and agreed to allow their blood to be used for research studies (Research related Studies Consent Form, see Appendix J), Peripheral blood will be collected prior to treatment for analysis of FcR polymorphisms. 20ml of peripheral blood in two yellow (ACD) or purple (EDTA) top Vacutainer[®] tubes. The tubes should be inverted 8-10 times to mix the tube additive and then refrigerated until shipped. Samples should be labeled with the patient's initials, study number, patient study ID# and date and time of collection. A log sheet (Correlative Science Form A) must be sent with the specimen and a copy retained in the investigator's file. This sample can be obtained at baseline, or at any time during a subject's participation in this study.

3.6.3 Peripheral Blood and Plasma Sample Procurement

If a patient has consented and agreed to allow their blood to be used for research studies 8 green top (heparin) tubes and 1 red top tube will be collected at the following timepoints: prior to treatment, prior to beginning Cycle 3 of treatment, and prior to beginning Cycle 6. If the 3rd blood/plasma sample is missed (i.e. prior to beginning Cycle 6), it can be drawn at a later time point. Samples should be labeled with the patient's initials, study number, patient study ID# and date and time of collection. A completed "Clinical Research Sample – Information and Processing Record" from the Human Immunology Core must be sent with the specimen and a copy of Correlative Science Form B should be retained in the patient's study chart.

Peripheral blood for MRD analysis in subjects with extended remissions will be collected as 3mL in EDTA tube. This will be performed during a routine blood draw. This will only be performed if the patient has consented and agreed to allow their blood to be used for research studies.

3.6.5 Paraffin-embedded tissue block submission

If a patient has consented to allow their tissue to be kept for future unknown use, only one tissue block will be needed to accommodate both histological confirmation and future correlative science studies. At time of progression or relapse, if a patient has consented to allow their tissue to be kept for future unknown use, and if a biopsy has been performed, these pathology specimens will be sent for pathology review and future correlative science studies to:

Tumor Tissue Bank Core Facility
Hospital of the University of Pennsylvania
Department of Pathology & Laboratory Medicine
[name]
[name]

[contact]
 [contact]

4 Subject Selection and Withdrawal

4.1 Inclusion Criteria

- **Documentation of disease**
 - Previously treated, histological confirmed follicle center lymphoma, grade 1-3a, marginal zone lymphoma, small lymphocytic lymphoma with < 5000 lymphocytes /mm³ or lymphoplasmacytic lymphoma with <3gm/ml IgM, mantle cell lymphoma by WHO classification (see Appendix F).
 - Bone marrow biopsies as sole means of diagnosis are not acceptable. Fine needle aspirates are not acceptable.
 - Institutional flow cytometry or immunohistochemistry must document CD20 antigen expression. Past documentation of CD20 antigen expression is admissible.
- **Prior treatment**
 - Patients must have been treated with rituximab in combination with chemotherapy or as monotherapy and must have refractory or progressive disease. Subjects must have had less than a partial response or progressive disease within 6 months of any dose of rituximab.
- Age ≥ 18
- ECOG performance status 0-2 (see Appendix B)
- Measurable disease must be present either on physical examination or imaging studies. Non-measurable disease alone is not acceptable. Any tumor mass $> 2\text{cm}$ is considered measurable.
- Lesions that are considered non-measurable, but assessable include the following:
 - Bone lesions (lesions if present should be noted)
 - Ascites
 - Pleural/pericardial effusion
 - Lymphangitis cutis/pulmonis
 - Bone marrow (involvement by non-Hodgkin lymphoma should be noted)
- Patients with a history of intravenous drug abuse or any behavior associated with increased risk of HIV infection should be tested for exposure to the HIV virus.

- Understand and voluntarily sign an informed consent form.
- Able to take aspirin (81 or 325 mg) daily as prophylactic anticoagulation. Patients intolerant to ASA may use warfarin or low molecular weight heparin
- Laboratory test results within these ranges:
 - Absolute neutrophil count $\geq 1000/\text{mm}^3$
 - Platelet count $\geq 75,000/\text{mm}^3$
 - Serum creatinine $\leq 2.0 \text{ mg/dL}$
 - Total bilirubin $\leq 1.5 \text{ mg/dL}$ (unless due to Gilbert's syndrome)
 - AST (SGOT) and ALT (SGPT) $\leq 2.5 \times \text{ULN}$ or $\leq 5 \times \text{ULN}$ if hepatic metastases are present.
- Disease free of prior malignancies for ≥ 5 years with exception of currently treated basal cell or squamous cell carcinoma of the skin, or carcinoma "in situ" of the cervix or breast.
- All study participants must be registered into the mandatory Revlimid REMS® program, and be willing and able to comply with the requirements of Revlimid REMS®.
- Females of childbearing potential (FCBP)[†] must have a negative serum or urine pregnancy test with a sensitivity of at least 50 mIU/mL within 10 – 14 days prior to and again within 24 hours of prescribing lenalidomide (prescriptions must be filled within 7 days) and must either commit to continued abstinence from heterosexual intercourse or begin TWO acceptable methods of birth control, one highly effective method and one additional effective method AT THE SAME TIME, at least 28 days before she starts taking lenalidomide. FCBP must also agree to ongoing pregnancy testing. Men must agree to use a latex condom during sexual contact with a FCBP even if they have had a successful vasectomy. See Appendix: Risks of Fetal Exposure, Pregnancy Testing Guidelines and Acceptable Birth Control Methods.

4.2 Exclusion Criteria

- Any serious medical condition, laboratory abnormality, or psychiatric illness that would prevent the subject from following study procedures.

[†] A female of childbearing potential is a sexually mature woman who: 1) has not undergone a hysterectomy or bilateral oophorectomy; or 2) has not been naturally postmenopausal for at least 24 consecutive months (i.e., has had menses at any time in the preceding 24 consecutive months).

- Pregnant or breast-feeding females. (Lactating females must agree not to breast feed while taking lenalidomide).
- Any condition, including the presence of laboratory abnormalities, which places the subject at unacceptable risk if he/she were to participate in the study or confounds the ability to interpret data from the study.
- Use of any other experimental drug or therapy within 28 days of baseline.
- Known hypersensitivity to thalidomide.
- The development of erythema nodosum if characterized by a desquamating rash while taking thalidomide or similar drugs.
- Any prior use of lenalidomide.
- Known positive for HIV or active infectious hepatitis, type A, B or C. Patients who test positive or who are known to be infected are not eligible due to an increased risk of infection with this regimen. An HIV test is not required for entry in this protocol, but is required if the patient is perceived to be at risk.
- Known CNS involvement by lymphoma.

4.3 Subject Recruitment and Screening

This clinical trial can fulfill its objectives only if patients appropriate for the trial are enrolled. All relevant medical and other considerations should be taken into account deciding whether this protocol is appropriate for a particular patient. Physicians should consider the risks and benefits of any therapy and therefore only enroll patients for whom the agents administered are appropriate. Although they will not be considered as formal eligibility (exclusion) criteria, as part of the decision-making process physicians should recognize that the following might increase the risk to the patients entering this protocol:

Serious medical illness or psychiatric condition, which would prevent compliance with treatment or informed consent.

Medical conditions such as uncontrolled infection, uncontrolled diabetes mellitus or cardiac disease, which, in the opinion of the treating physician, would make this protocol unreasonably hazardous for the patient.

Patients at high risk of hepatitis B infection should be screened before starting treatment. Carriers of hepatitis B should be closely monitored for evidence of active HBV infection and hepatitis during and for several months after rituximab treatment.

Lenalidomide increases the risk of thrombotic events in patients who are at high risk or with a history a thrombosis, in particular when combined with other drugs known to cause thrombosis. When lenalidomide is combined with other agents such as steroids (e.g. dexamethasone,

prednisone), anthracyclines (Doxil, Adriamycin) and erythropoietin the risk of thrombosis is increased. Due to the known increased risk of thrombotic events associated with the combination of lenalidomide and dexamethasone subjects will receive aspirin (81 or 325 mg) or some other form of prophylaxis as deemed appropriate. Low molecular weight heparin may be utilized in patients that are intolerant to ASA. Coumadin should be used with caution and close monitoring of INR.

Patients with absolute lymphocyte count >20,000/ul should be closely monitored for tumor lysis syndrome. These patients should receive appropriate supportive care and prophylaxis (e.g., allopurinol, intravenous hydration, additional laboratory test monitoring, etc.) prior to rituximab infusion. A modified dosing scheme is suggested for those patients with absolute lymphocyte count >20,000/ul (see 6.2).

4.4 Early Withdrawal of Subjects

Subjects will be removed from protocol for any of the following reasons:

[figure not shown]
- Any clinical adverse event, laboratory abnormality or inter-current illness, which, in the opinion of the investigator, indicates that, continued treatment with study therapy is not in the best interest of the subject.
- Any toxicity requiring discontinuation as outlined in the dose modifications criteria in Table 2, Section 6.1.3.
- The subject declines further therapy.
- The subject experiences progression of disease after the first 2 cycles of study treatment (Part I) with estimated life expectancy < 3 months or relapse of lymphoma/progression of disease after having received rituximab (see also Section 7).
- It is deemed in the best interest of the subject. In this instance, the Principal Investigator should be notified.
- Termination of the study by the supporter, Celgene.
- Pregnancy
- The reason(s) for withdrawal should be noted in the case report form and in the subject's medical record. Survival data on patients that withdraw from the trial will be recorded. Statistical analysis will be performed on an intent-to-treat basis.

5 Drug Formulation, Availability and Preparation

5.1 Lenalidomide

REVLIMID® (Lenalidomide), a thalidomide analogue, is an immunomodulatory agent with anti-angiogenic properties. The chemical name is 3-(4-amino-1-oxo 1,3-dihydro -2H-isoindol-2-yl) piperidine-2,6-dione and it has the following chemical structure:

Chemical Structure of Lenalidomide

3-(4-amino-1-oxo 1,3-dihydro-2H-isoindol-2-yl) piperidine-2,6-dione

The empirical formula for lenalidomide is C₁₃H₁₃N₃O₃, and the gram molecular weight is 259.3.

Lenalidomide is off-white to pale-yellow solid powder. It is soluble in organic solvent/water mixtures, and buffered aqueous solvents. Lenalidomide is more soluble in organic solvents and low pH solutions. Solubility was significantly lower in less acidic buffers, ranging from about 0.4 to 0.5 mg/ml. Lenalidomide has an asymmetric carbon atom and can exist as the optically active forms S(-) and R(+), and is produced as a racemic mixture with a net optical rotation of zero.

5.1.1 Mechanism of Action

The mechanism of action of lenalidomide remains to be fully characterized. Lenalidomide possesses immunomodulatory and anti-angiogenic properties. Lenalidomide inhibited the secretion of pro-inflammatory cytokines and increased the secretion of anti-inflammatory cytokines from peripheral blood mononuclear cells. Lenalidomide inhibited cell proliferation with varying effectiveness (IC₅₀s) in some but not all cell lines. Of cell lines tested, lenalidomide was effective in inhibiting growth of Namalwa cells (a human B cell lymphoma cell line with a deletion of one chromosome 5) but was much less effective in inhibiting growth of KG-1 cells (human myeloblastic cell line, also with a deletion of one chromosome 5) and other cell lines without chromosome 5 deletions. Lenalidomide inhibited the expression of cyclooxygenase-2 (COX-2) but not COX-1 in vitro.

5.1.2 Pharmacokinetics and Drug Metabolism

Absorption:

Lenalidomide, in healthy volunteers, is rapidly absorbed following oral administration with maximum plasma concentrations occurring between 0.625 and 1.5 hours post-dose.

Co-administration with food does not alter the extent of absorption (AUC) but does reduce the maximal plasma concentration (C_{max}) by 36%. The pharmacokinetic disposition of lenalidomide is linear. C_{max} and AUC increase proportionately with increases in dose. Multiple dosing at the recommended dose-regimen does not result in drug accumulation.

Pharmacokinetic sampling in myelodysplastic syndrome (MDS) patients was not performed. In multiple myeloma patients, maximum plasma concentrations occurred between 0.5 and 4.0 hours post-dose both on Days 1 and 28. AUC and Cmax values increase proportionally with dose following single and multiple doses. Exposure (AUC) in multiple myeloma patients is 57% higher than in healthy male volunteers.

Distribution:

In vitro (¹⁴C)-lenalidomide binding to plasma proteins is approximately 30%.

Metabolism and Excretion:

The metabolic profile of lenalidomide in humans has not been studied. In healthy volunteers, approximately two-thirds of lenalidomide is eliminated unchanged through urinary excretion. The process exceeds the glomerular filtration rate and therefore is partially or entirely active. Half-life of elimination is approximately 3 hours.

5.1.3 Supplier

Celgene Corporation will supply Revlimid® (lenalidomide) to study participants at no charge through the Revlimid REMS® program. All physicians who prescribe lenalidomide for research subjects enrolled into this trial and all research subjects enrolled into this trial must be registered in and must comply with all requirements of Celgene's Revlimid REMS® program.

5.1.4 Dosage form

Lenalidomide will be supplied as capsules for oral administration.

5.1.5 Packaging

Lenalidomide will be shipped directly to patients. Bottles will contain a sufficient number of capsules for one cycle (28 days) of dosing.

5.1.6 Storage

Lenalidomide should be stored at room temperature away from direct sunlight and protected from excessive heat and cold.

5.1.7 Prescribing Information

Lenalidomide (Revlimid®) will be provided to research subjects for the duration of their participation in this trial at no charge to them or their insurance providers. Lenalidomide will be provided in accordance with the Revlimid REMS® program. Per standard Revlimid REMS® requirements all physicians who prescribe lenalidomide for research subjects enrolled into this trial, and all research subjects enrolled into this trial must be registered in and must comply with all requirements of Celgene's Revlimid REMS® program. Prescriptions must be filled within 7 days. ***Only enough lenalidomide for one cycle of therapy will be supplied to the patient each cycle.***

5.1.8 Special Handling Instructions

Females of childbearing potential should not handle or administer lenalidomide unless they are wearing gloves.

5.2 Rituximab (Rituxan®, IDEC-C2B8)

Rituximab is clinically indicated for the treatment of CD20+ non-Hodgkin lymphomas, and will be billed to the patient and/or insurance. Please refer to the agent's package insert for additional information.

5.2.1 Availability

Rituximab is commercially available in 10ml and 50ml single-use vials containing 100 or 500 mg of antibody, respectively at concentration of 10 mg/ml.

5.2.2 Storage and Stability

Intact vials should be stored under refrigeration. Dilute solutions for infusion (1-4mg/ml) are stable for 24 hours under refrigeration, and for an additional 24 hours at room temperature.

5.2.3 Preparation

The desired dose of rituximab should be diluted in 0.9% NaCL or D5W to a final concentration of 1-4mg/ml. Mix by inverting the bag gently.

5.2.4 Administration

Rituximab will be administered by IV infusion as described in 6.2. Patients must be pretreated with acetaminophen and diphenhydramine prior to each dose of rituximab.

5.2.5 Toxicity

The most serious adverse events associated with rituximab include severe infusion reactions, Tumor Lysis syndrome and severe muco-cutaneus reactions. Severe infusion reactions consisting of hypoxia, pulmonary infiltrates, acute respiratory distress syndrome, myocardial infarction, ventricular fibrillation or cardiogenic shock may be fatal. Most reported fatal reactions occurred within 24 hours of the first dose of rituximab. If a reaction occurs, the infusion should be stopped until the symptoms resolve, and then restarted at a 50% slower rate. Because severe infusion reactions have been noted more frequently in patients with high leukocyte counts, such patients should be observed closely.

Tumor Lysis syndrome resulting in renal failure has been described and occasional fatalities noted. Tumor Lysis syndrome is more likely in patients with high numbers of circulating malignant cells. These patients should receive appropriate supportive care and prophylaxis (e.g., allopurinol, intravenous hydration, additional laboratory test monitoring, etc.) prior to rituximab infusion.

Severe muco-cutaneus reactions associated with rituximab include Stevens-Johnson syndrome and toxic epidermal necrolysis. The onset of these reactions has been from 1-3 weeks.

Less severe infusion reactions are common with rituximab. These include fever, chills and dyspnea. The mechanism of rituximab infusion reactions is thought to be the release of cytokines. Infusions should be interrupted until symptoms resolve, and restarted at a 50% slower

rate. Pretreatment with acetaminophen and diphenhydramine before each dose of rituximab may minimize the likelihood/severity of infusion reactions.

Recent reports describe hepatitis B reactivation with fulminant hepatitis, hepatic failure and death in some patients receiving rituximab in combination with chemotherapy. The median time to diagnosis of hepatitis was approximately 4 months after starting rituximab and approximately 1 month after last dose.

A report in the literature described an increase in fatal infection in HIV-related lymphoma patients when rituximab was used in combination with CHOP chemotherapy, as compared to CHOP alone. Patients with HIV infection are not eligible for entry on this research study.

6 Dose Modifications and Management of Toxicities

6.1 Lenalidomide and Dexamethasone

Administration: For subjects in both Cohorts 1 and 2 with baseline creatinine clearance of >30 ml/min, the initial dose of lenalidomide for investigation is 10 mg/day, orally on days 1 - 28, repeated every 28 days (28 day cycle). The initial dose for subjects with a baseline creatinine clearance of <30 ml/min will be 5 mg orally on days 1 – 28 of each 28 day cycle. Dosing will be at approximately the same time each day. Prescriptions must be filled within 7 days.

For patients in Cohort 1 only, the initial dexamethasone dose will be 8mg PO once weekly (dosing on days 3, 10, 17 and 24 are suggested but not required), repeated every 28 days.

Subjects enrolled to Cohort 2 will not receive dexamethasone as part of protocol therapy.

If a dose of lenalidomide is missed, it should be taken as soon as possible on the same day. If it is missed for the entire day, it should not be made up.

Patients who take more than the prescribed dose of lenalidomide should be instructed to seek emergency medical care if needed and contact study staff immediately.

Subjects experiencing adverse events may need study treatment modifications (See 6.1.3).

Lenalidomide Dose Escalation Evaluation and Instruction: All subjects shall be evaluated after first cycle of lenalidomide for dose escalation. If no drug-related toxicity of \geq Grade 3 was noted, dose escalation to the next dose level is permissible at the start of Cycle 2 during Part I (see Section 6.1.1 for lenalidomide dose levels). No dose escalation shall be permitted upon entry into Part II of the trial or at any other time except at the start of Cycle 2 during Part I.

Record of administration: Accurate records of all study drug administration (including prescribing and dosing) will be made in the source documents.

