6.1.1 Dose Continuation, Modification and Interruption

Subjects will be evaluated for AEs at each visit with the NCI CTCAE v5.0 (Appendix C: NCI CTCAE v5.0) used as a guide for the grading of severity. Refer to the Dose Modification Steps below, and to Sections 6.1.2 and 6.1.3 for full instruction on initiation of a new cycle of therapy and dose modifications during a cycle of therapy.

Dose Modification Steps

Table 1: LENALIDOMIDE Dose Reduction Steps	
Dose Level +1	15 mg daily on Days 1-28 every 28 days
Starting Dose	10 mg daily on Days 1-28 every 28 days
Dose Level – 1	5 mg daily on Days 1-28 every 28 days
Dose Level – 2	5 mg every other day during Days 1-28 every 28 days
Dose Level - 3	Subjects with extended remissions (response > 1 year) may have their dose adjusted at the discretion of the Principal Investigator; any dose adjustments at Dose Level -3 must be approved in writing by the Medical Monitor.

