6.1.2 Instructions for initiation of a New Cycle

A new course of treatment may begin on the scheduled Day 1 of a new cycle if:

- The ANC is $\geq 1000 /mm^3$
- The platelet count is $\geq 50,000 /mm^3$;
- Any drug-related rash or neuropathy that may have occurred has resolved to \leq grade 1 severity;
- Any other drug-related adverse events that may have occurred have resolved to \leq grade 2 severity.

If these conditions are not met on Day 1 of a new cycle, the subject will be evaluated weekly and a new cycle of treatment will not be initiated until the toxicity has resolved as described above. If lenalidomide dosing was halted during the previous cycle and was restarted with a one-level dose reduction without requiring an interruption for the remainder of the cycle, then that reduced dose level will be initiated on Day 1 of the new cycle. **If lenalidomide dosing was omitted for the remainder of the previous cycle or if the new cycle is delayed due to toxicity newly encountered on the scheduled Day 1, then the new cycle will be started with a one-level dose reduction of lenalidomide.**

If subjects experience cytopenias and do not meet study requirements to resume lenalidomide, they may proceed with rituximab as described in the protocol.

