Desquamating (blistering) rash- any Grade	
 Discontinue lenalidomide. Remove patient from study. 	
 Discontinue lenalidomide. Remove patient from study.

Table 2: Lenalidomide Dose Modifications

NCI CTC Toxicity Grade	Onset Day 2-21 of Cycle	Onset \geq Day 22 of Cycle
Neuropathy Grade 3	
 Hold (interrupt) lenalidomide dose. Follow at least weekly. If the toxicity resolves to \leq grade 1 prior to Day 21, restart lenalidomide at next lower dose level and continue the cycle through Day 28. 	
 Omit lenalidomide for the remainder of the cycle. See Instructions for Initiation of a New Cycle and reduce the dose of lenalidomide by 1 dose level.
Grade 4	
 Discontinue lenalidomide. Remove patient from study. 	
 Discontinue lenalidomide. Remove patient from study.
Venous thrombosis/embolism \geq Grade 3	
 Hold (interrupt) lenalidomide and start anticoagulation; restart lenalidomide at investigator's discretion (maintain dose level). 	
 Omit lenalidomide for remainder of cycle.
Hyperthyroidism or hypothyroidism	
 Omit lenalidomide for remainder of cycle, evaluate etiology, and initiate appropriate therapy. See Instructions for Initiation of a New Cycle and reduce the dose of lenalidomide by 1 dose level. 	
 Omit lenalidomide for remainder of cycle, evaluate etiology, and initiate appropriate therapy. See Instructions for Initiation of a New Cycle and reduce the dose of lenalidomide by 1 dose level.
other non-hematologic toxicity \geq Grade 3 attributable to lenalidomide	
 Hold (interrupt) lenalidomide dose. Follow at least weekly. If the toxicity resolves to \leq grade 2 prior to Day 21, restart lenalidomide at next lower dose level and continue the cycle through Day 28. 	
 Omit lenalidomide for remainder of cycle. See Instructions for Initiation of a New Cycle and reduce the dose of lenalidomide by 1 dose level.

NOTE: If subjects do not have adequate hematological recovery within 28 days of their last study treatment, lenalidomide will be discontinued and not restarted. However, the subjects will still be followed for response assessment and included in endpoint analyses.

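### The Cycle 2 lenalidomide escalation rule has no renal condition, so a 5 mg start given for creatinine clearance below 30 ml/min may be raised to 10 mg with clearance unchanged; Section 3.1 also omits the renal start

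*Combined protocol and SAP*

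**What the plan says.** Section 6.1 sets two starting doses by baseline creatinine clearance: 10 mg daily above 30 ml/min, and a lower dose below it: "The initial dose for subjects with a baseline creatinine clearance of <30 ml/min will be 5 mg orally". Later in the same section comes the escalation rule: "All subjects shall be evaluated after first cycle of lenalidomide for dose escalation". If Cycle 1 showed no drug-related toxicity of Grade 3 or higher, "dose escalation to the next dose level is permissible at the start of Cycle 2 during Part I". Cycle 2 is the only opportunity: "No dose escalation shall be permitted upon entry into Part II of the trial or at any other time", with the start of Cycle 2 as the sole exception.

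Table 1 in Section 6.1.1 gives the ladder. The row for 5 mg daily is Dose Level -1. The row directly above it, labelled the starting dose, is "10 mg daily on Days 1-28 every 28 days". Dose Level +1 is 15 mg.

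Section 1.4 likewise ties the one-level increase to the patient's tolerance and refers to Section 6. Section 3.1 states a 10 mg start for subjects in both cohorts and names 15 mg as the escalated dose. It points to Section 6 for the definition of tolerance and for the Part II dose, and does not mention the 5 mg renal start.

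**The concern.** The lower start depends on clearance alone. Section 5.1.2 supplies a plausible reason: in healthy volunteers about two-thirds of the drug leaves unchanged in the urine. The test for escalation is a different one, namely absence of severe drug-related toxicity over one 28-day cycle. That cycle shows tolerance of 5 mg. It does not show whether clearance has changed, and it does not show tolerance of 10 mg.

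A subject could therefore return to the dose that the renal rule withheld while the reason for withholding it still applies. What is at stake is the safety of a few subjects in a population that Section 1.4 describes as heavily pre-treated and at risk of myelosuppression. In addition, a reader who works from Section 3.1 alone would start such a subject at twice the dose that Section 6.1 sets.

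**Working it through.** The plan gives no figure to reproduce here. The check is a reading of the rules side by side, the arithmetic of the dose ladder, and a test of whether such subjects can enrol.

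**1. Is there a renal condition anywhere on the path from 5 to 10 mg?**

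- Section 6.1, escalation: no drug-related toxicity of Grade 3 or higher. No renal item.
- Section 6.1.2, "A new course of treatment may begin on the scheduled Day 1 of a new cycle if": neutrophils, platelets, rash or neuropathy, and other drug-related events. No creatinine or clearance item.
- Section 6.1.3, Table 2: no renal-function row. The closest is the catch-all for "other non-hematologic toxicity", which needs Grade 3 or higher attributable to lenalidomide.
- Section 11.2: the Medical Monitor reviews adverse events and other safety data before escalation. No renal criterion is given.
- Section 3.3: serum creatinine is scheduled before each of Cycles 1-6, but no dosing rule uses the Cycle 2 value.

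Clearance enters the dosing rules once, for the initial dose.

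**2. Size of the step (doses from 6.1 and Table 1).**

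- 5 mg starter: 10/5 = 2.0, or +100%.
- 10 mg starter: 15/10 = 1.5, or +50%.
- Renal reduction against the standard start: 1 - 5/10 = 50% in Cycle 1; 1 - 10/10 = 0% after the step.

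**3. Exposure.** Section 5.1.2 says that "AUC increase proportionately with increases in dose" for healthy volunteers, and makes a similar statement for myeloma patients. Carrying this below 30 ml/min is an assumption. With clearance unchanged, the subject's own AUC would then rise by a factor of 2.0, against 1.5 for a 10 mg starter.

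**4. Can such subjects enrol?** Section 4.1 caps serum creatinine at 2.0 mg/dL and sets no clearance floor. The protocol names no clearance formula, so Cockcroft-Gault is assumed: (140 - age) × weight / (72 × creatinine), times 0.85 for women.

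| Creatinine (mg/dL) | Age | Weight (kg) | Man (ml/min) | Woman (ml/min) |
|---|---|---|---|---|
| 2.0 | 70 | 60 | 29.2 | 24.8 |
| 2.0 | 80 | 50 | 20.8 | 17.7 |
| 2.0 | 60 | 80 | 44.4 | 37.8 |
| 1.5 | 80 | 50 | 27.8 | 23.6 |

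First row: (140 - 70) × 60 / (72 × 2.0) = 29.2, and 0.85 × 29.2 = 24.8. At creatinine 2.0, over ages 60-80 and weights 50-80 kg, clearance runs from about 17.7 to 44.4 ml/min. Some eligible subjects near the cap fall below 30 and others do not.

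**5. Section 3.1 against Section 6.1.** Section 3.1 gives every subject 10 mg and an escalated dose of 15 mg; 6.1 gives some subjects 5 mg and one level up. For the renal subgroup these cannot both hold.

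**The case against.** The best defence is that this is titration to tolerance, and deliberate. The renal start and the rule for all subjects stand in the same section, clearance is linked only to the initial dose, and nothing says the reduction must last. A low start followed by one optional step after a clean cycle is a coherent rule. This stands as a possible reading, and the documents do not exclude it. They also do not say it is intended for these subjects, and one sentence would settle the matter.

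Second, Table 1 is headed as a list of reduction steps and does not expressly place the renal 5 mg start at Dose Level -1, so the 10 mg target is an inference. That is correct. Still, 10 mg is the row directly above 5 mg, and no other row fits the next level as naturally.

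Third, controls exist: the Grade 3 criterion, the new-cycle thresholds, weekly blood counts through Cycle 6, the holds in Table 2, Medical Monitor review, and a creatinine value in hand before Cycle 2. They limit the harm, but none makes escalation depend on renal function.

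Fourth, the absolute step is 5 mg in both cases, and the factors 2.0 and 1.5 are only ratios of adjacent rows. This also stands: no toxicity risk has been estimated from them.

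A reader might infer that after escalation the dose can fall only for toxicity. The documents do not support that. Dose Level -3 allows discretionary adjustment in responses beyond one year, and Section 4.4 allows removal for a laboratory abnormality, an intercurrent illness or the subject's best interest.

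**Conclusion.** The point holds as a gap in a dosing rule. Followed as written, Section 6.1 permits a renal dose reduction to be reversed after one cycle with clearance unchanged, by a step of +100%. Section 3.1 conflicts with the renal start. This rests on reading 10 mg as the level above 5 mg; the doubling of exposure rests further on dose-proportional AUC below 30 ml/min.

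Three stronger conclusions are not supported:

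- The plan does not require the doubling. Escalation is optional and conditional.
- The plan does not authorise a rise from 5 to 15 mg. Section 3.1 taken literally would give 15/5 = 3.0, but Section 6.1 allows only the next level.
- The trial's results are not put in doubt. No endpoint, analysis or power figure changes. The number of affected subjects is not given and is probably small under the creatinine cap.

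This is a cheap safety improvement worth considering, not a defect that blocks the trial.

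**What to change.** In Section 6.1, state that subjects started at 5 mg for clearance below 30 ml/min are not escalated at Cycle 2 unless clearance, recalculated from the scheduled pre-Cycle 2 creatinine, is at least 30 ml/min, and that their maximum is then 10 mg. In Section 3.1, add the 5 mg renal start and replace the 15 mg figure with the next dose level under 6.1.1, subject to the renal rule in 6.1. If titration to tolerance below 30 ml/min is intended, say so in 6.1 instead.

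Two side drafting points can be settled in the same edit: name the clearance formula, and assign a dose at exactly 30 ml/min, which the present limits leave out.

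The cost is a sentence in 6.1, two wording changes in 3.1, and one calculation per affected subject. No new blood test is needed. The downside is that a subject whose clearance stays below 30 ml/min but who tolerates 5 mg loses the option of a higher dose. The gate also rests on a single recalculated value, so a change from 29 to 30 ml/min that is only measurement noise would still open the step; the baseline rule has the same weakness.
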